1.5.3 Stable Disease

To satisfy criteria for SD, all of the following conditions must be attained:

- No evidence of new disease
- Neither sufficient tumor shrinkage from baseline to qualify for PR nor sufficient evidence of tumor growth to qualify for PD
- If PET-CT performed, the results show a score of 4 (uptake moderately > liver) or score of 5 (uptake markedly > liver) on the Deauville 5-point scale with no significant change in uptake compared with baseline.

1.5.4 Progressive Disease

The occurrence of any of the following events indicates progressive disease (PD):

- Evidence of any new disease that was not present at baseline:
 - A new node that measures > 1.5 cm in any diameter
 - A new node that measures > 1.0 cm to ≤ 1.5 cm in the LD and > 1.0 cm in the LPD
 - Reappearance of an extranodal lesion that had resolved (i.e., had previously been assigned a PPD of 0 cm²)
 - o A new extranodal lesion of any size
 - New non-index disease (e.g., effusions, ascites, or other organ abnormalities) of any size unequivocally attributable to lymphoma (usually requires PET, biopsy, cytology, or other non-radiologic confirmation to confirm disease attributable to lymphoma). Note: Isolated new effusions, ascites, or bone lesions are not sufficient evidence alone of PD unless histologically confirmed. In patients with no prior history of pulmonary lymphoma, new lung nodules identified by CT are usually benign. Thus, a declaration of PD should not be made if this is the only manifestation of an apparently new lesion.
 - New FDG-avid foci consistent with lymphoma rather than another etiology (e.g., infection, inflammation). If there is uncertainty regarding the etiology of new lesions, biopsy or interval scan may be considered.
 - New or recurrent bone marrow involvement with lymphoma by PET-CT or by bone marrow biopsy if prior PET-CT or bone marrow biopsy performed as part of the study was negative for lymphoma.
- Evidence of worsening of nodal or extranodal index lesions:
 - Increase from the nadir by \geq 50% in the SPD of index lesions
 - Evidence of worsening of individual index lymph nodes or nodal masses:
 - Increase from the nadir by ≥ 50% in the PPD for any individual node if the node now has an LD of > 1.5 cm and there is an absolute change from the nadir of ≥ 0.5 cm in the LD or LPD and to an absolute dimension of ≥ 2.0 cm.

Version 9, 18 Feb 2020

- Increase from the nadir by ≥ 50% in the LD for any individual node if the node now has an LD of > 1.5 cm and there is an absolute change from the nadir of > 0.5 cm in the LD
- Increase from the nadir by ≥ 50% in the LPD for any individual node if the node now has an LPD of > 1.5 cm and there is an absolute change from the nadir of ≥ 0.5 cm in the LPD
- If a lesion had been classified as a small lymph node, there is an additional requirement that the lesion has an LD of > 1.0 cm and an LPD of > 1.0 cm
- Unequivocal increase in the size of non-index disease
- \circ Unequivocal worsening in the size of the liver or spleen (with the additional condition that there must be ≥ 1 nodule present in the enlarging organ)
- Transformation to a more aggressive NHL histology as established by lymph node biopsy
- If PET performed, there is a score of 4 (uptake moderately > liver) or score of 5 (uptake markedly > liver) on the Deauville 5-point scale with an increase in uptake compared with the nadir in conjunction with an anatomic increase in lesion size consistent with PD.

Note: Study subjects undergoing PET for lymphoma assessment can experience transient disease flare on imaging before having subsequent therapy-induced tumor regression. Worsening of constitutional symptoms or performance status in the absence of objective evidence of worsening lymphoma (e.g., due to infection) may not represent definitive disease progression. Further, transient worsening of disease during temporary interruptions of study therapy (e.g., for drug-related toxicity or inter-current illness) may not indicate definitive progressive lymphoma. If there is uncertainty regarding whether there is true lymphoma progression and if medically appropriate, the subject may continue or resume study treatment and remain under close observation (e.g., evaluated at 3- to 6-week intervals) while relevant radiographic, clinical, and/or laboratory assessments are performed to document whether tumor control can be maintained or whether disease progression has truly occurred. If subsequent evaluations suggest that the subject has experienced persistent definitive disease progression, then the date of progression will be the timepoint at which progression was first objectively documented.

1.5.5 Nonevaluable

In a subject who does not have evidence of PD, the occurrence of any of the following conditions indicates a response status of NE:

- There are no images or inadequate or missing images, defined as the inability to visualize > 25% of index disease and > 50% of non-index disease.
- 2 Chronic Lymphocytic Leukemia/Small Lymphocytic Lymphoma

2.1 Tumor Assessment Criteria

The determination of CLL/SLL response and progression will be based on standardized criteria [Hallek 2008], as recently updated [Cheson 2012].

Version 9, 18 Feb 2020

2.2 Method of Assessment

In addition to clinical examination, imaging-based evaluation will be used in this study in all subjects enrolled. CT scan is the preferred method for radiographic tumor assessment. MRI scanning may be used at the investigator's discretion in subjects for whom this may be a preferred alternative to CT scanning; however, if MRI is performed, a non-contrast CT of the chest should be performed. Contrast-enhanced scanning is preferred, but iodine-containing or gadolinium contrast material may be omitted in subjects for whom use of a contrast agent would be medically contraindicated. Chest x-ray, ultrasound, endoscopy, laparoscopy, PET, radionuclide scans, or tumor markers will not be considered for response assessment.

For radiographic evaluations, the same method of assessment and the same technique (e.g., scan type, scanner, subject position, dose of contrast, injection/scan interval) should be used to characterize each identified and reported lesion at baseline and during study treatment and follow-up. However, if a subject is imaged without contrast at baseline, subsequent assessments should be performed with contrast, unless the subject cannot tolerate the contrast.

All relevant clinical and radiographic information required to make each tumor status assessment must be made available for source verification as requested by the study sponsor.

2.3 Timing of Assessments

During screening, clinical, laboratory, and imaging-based tumor assessments should be performed within the specified screening period. Clinical tumor assessments should be performed at each designated clinical visit. On-study CT/MRI tumor assessments should be performed as indicated in Section Changed. An end-of-study CT/MRI tumor assessment should be performed unless the subject already has radiographic confirmation of disease progression ≤ 4 weeks prior. If a subject permanently discontinues study drug prior to objective documentation of CLL/SLL progression, investigators should optimally attempt to obtain further follow-up at ~12-week intervals until CLL/SLL progression is documented or until the initiation of a new post-study therapy for the subject's CLL/SLL.

2.4 Identification and Measurement of Tumor Lesions and Organomegaly

2.4.1 Index Lesions

At baseline, up to 6 lymph nodes should be selected as index lesions that will be used to quantitate the status of the disease during study treatment. Ideally, the index lesions should be located in disparate regions of the body. Only peripheral nodes need be selected as index lesions. However, it is optimal if mediastinal and retroperitoneal areas of disease are assessed whenever these sites are involved.

Index lesions will be measured and recorded at baseline and at the stipulated intervals. The cross-sectional dimensions (the largest cross-sectional diameter, i.e., the LD \times LPD) will be recorded (in cm) for each index lesion. The product of the perpendicular diameters (PPD) (in cm²) for each index lesion and SPD (in cm²) for all index lesions will be calculated and recorded. The baseline SPD will be used as references by which objective tumor response will be characterized during treatment. The nadir LD of individual lesions and the nadir

Version 9, 18 Feb 2020

SPD will be used as references by which CLL/SLL progression will be characterized. All LD and LPD diameters will be reported in centimeters and all PPDs and SPDs will be reported in centimeters squared.

A nodal mass may be selected as a nodal index lesion if it is both abnormal and measurable at baseline. A lymph node lesion is considered abnormal if it has a single diameter that is > 1.5 cm and is considered measurable if it has 2 perpendicular diameters that can be accurately measured in cross section with the LD being ≥ 1.0 cm and the LPD also being ≥ 1.0 cm.

Index lesions measuring > 1.5 cm in the LD, regardless of the measurement of the LPD, will be prioritized during baseline index lesion selection.

At follow-up timepoints, the LDs for individual lesions and the SPD of all nodal index lesions will be considered. Because nodal index lesions that have one or both diameters > 0 cm and < 1.0 cm cannot be reliably measured, a default value of 1.0 cm will be assigned for each diameter that meets these criteria and the resulting PPD will be used in SPD calculations. Based on this convention, a CR may be achieved even if an SPD value is > 0 cm², (i.e., if all lymph nodes measure < 1.0 cm²).

A new node that measures > 1.5 cm in any diameter or a new node that measures > 1.0 cm to ≤ 1.5 cm in the LD and measures > 1.0 cm in the LPD will be considered progressive disease.

In cases in which a large lymph node mass has split into multiple components, only those elements that are > 1.0 cm in ≥ 1 diameter will be considered abnormal and used in calculating the SPD. Progression of the lesion can only be based on the SPD of abnormal sub-components. Lesion sub-components that are considered normal but measurable will have the true PPDs calculated, with the result used only for calculating an accurate nadir. Similarly, lesion sub-components that are visible but neither abnormal nor measurable will have the default PPD of 1.0 cm 2 (1.0 cm \times 1.0 cm) stored only for the purposes of calculating the nadir SPD value.

If lesions merge, a boundary between the lesions will be established so the LD of each individual lesion can continue to be measured. If the lesions have merged in a way that they can no longer be separated by this boundary, the newly merged lesion will be measured bidimensionally.

2.4.2 Spleen and Liver

Both the spleen and liver will be assessed by CT/MRI scan and by physical examination at baseline and at the stipulated intervals during treatment. The baseline and nadir values for the longest vertical dimension (LVD) of each organ will be used as reference to further characterize the objective tumor response of the measurable dimensions of the CLL/SLL during treatment. All spleen and liver LVD measurements should be recorded in centimeters.

Physical examination of the spleen should comprise assessment of its LVD below the left costal margin by palpation. By physical examination, the spleen will be considered enlarged if it is palpable below the left costal margin. If the spleen is not palpable below the left costal margin, it should be assigned a value of 0 cm for physical examination

Version 9, 18 Feb 2020

assessment. By imaging, the spleen will be considered enlarged if it is > 12 cm in LVD [Bezerra 2005, Asghar 2011], with the LVD being obtained by multiplying the number of sections on which the spleen is visualized by the thickness of the sections (e.g., if the spleen is seen in 14 contiguous cross-sectional images with 0.5-cm thickness, the LVD is recorded as 7 cm).

For subjects with splenomegaly at baseline or at the splenic LVD nadir, respective response and progression evaluations of the spleen will consider only changes relative to the enlargement of the spleen (i.e., the portion of the LVD that is > 0 cm by physical examination or > 12 cm by imaging) at baseline or nadir, not changes relative to the total splenic LVD.

A 50% decrease from baseline (minimum decrease of 2 cm) in the enlargement of the spleen in its LVD or to \leq 12 cm by imaging, or regression to a spleen LVD of \leq 0 cm by physical examination, is required for declaration of a splenomegaly response. Conversely, an increase in splenic enlargement by \geq 50% (minimum increase of 2 cm) from nadir is required for declaration of splenic progression. Subjects with a normal spleen LVD (i.e., a LVD of \leq 0 cm by physical examination or \leq 12 cm by imaging) at nadir will only be considered to have progressed if the spleen attains a LVD of > 14 cm by imaging or > 2 cm by physical exam.

Physical examination of the liver should comprise assessment of its LVD at the right midclavicular line by percussion. By physical examination, the liver will be considered enlarged if it is > 15 cm in LVD as assessed by percussion [Walker 1990]. By imaging, the liver will be considered enlarged if it is > 18 cm in LVD [Erturk 2006].

A 50% decrease (minimum decrease of 2 cm) from baseline in the enlargement of the liver in its LVD or to \leq 18 cm by imaging, or regression to a liver LVD of \leq 15 cm by physical examination, is required for declaration of a hepatomegaly response. Conversely, an increase in liver enlargement by \geq 50% (minimum increase of 2 cm) from nadir is required for declaration of hepatic progression. Subjects with a normal liver LVD (i.e., a LVD of \leq 15 cm by physical examination or \leq 18 cm by imaging) at nadir will only be considered to have progressed if the liver attains a LVD of > 20 cm by imaging or > 17 cm by physical exam.

2.4.3 Non-Index Lesions

Any other measurable and abnormal nodal lesions not selected for quantitation as index lesions may be considered non-index lesions. In addition, non-measurable evidence of CLL/SLL such as nodal lesions with both diameters < 1.0 cm, extranodal lesions, bone lesions, leptomeningeal disease, ascites, pleural or pericardial effusions, lymphangitis of the skin or lung, abdominal masses that are not confirmed and followed by imaging techniques, cystic lesions, previously irradiated lesions, and lesions with artifacts may be considered as non-index disease.

The presence or absence of non-index disease should be recorded at baseline and at the stipulated intervals during treatment. If present at baseline, up to 6 non-index lesions should be recorded. The non-index disease at baseline will be used as a general reference to further characterize regression or progression of CLL/SLL during assessments of the

Version 9, 18 Feb 2020

objective tumor response during treatment. Measurements are not required and these lesions should be followed as "present" or "absent".

2.5 Definitions of Tumor Response and Progression

Responses will be categorized as complete response (CR), partial response (PR), stable disease (SD), or progressive disease (PD). In addition, a response category of nonevaluable (NE) is provided for situations in which there is inadequate information to otherwise categorize response status.

The best overall response will be determined. The best overall response is the best response recorded from the start of treatment until disease/recurrence progression (taking as a reference for disease progression the smallest measurements recorded since treatment started). Subjects with a best overall response of NE or ND will be counted in the denominators in calculations of tumor response rates. Where imaging data are available, these data will supersede physical examination data in determining tumor status.

2.5.2 Complete Response and Complete Response with Incomplete Blood Count Recovery

To satisfy criteria for CR or CRi, all of the following conditions must be attained:

- No evidence of new disease
- Absolute lymphocyte count (ALC) in peripheral blood of $< 4 \times 10^9/L$
- Regression of all index nodal masses to normal size ≤ 1.5 cm in the LD
- Normal spleen and liver size
- Regression to normal of all nodal non-index disease and disappearance of all detectable non-nodal, non-index disease
- Morphologically negative bone marrow defined as < 30% of nucleated cells being lymphoid cells and no lymphoid nodules in a bone marrow sample that is normocellular for age
- Peripheral blood meeting all of the following criteria:
 - ANC \ge 1.5 x 10⁹/L without need for exogenous growth factors (e.g., G-CSF)
 - Platelet count $\ge 100 \times 10^9$ /L without need for exogenous growth factors
 - Hemoglobin \geq 110 g/L (11.0 g/dL) without red blood cell transfusions or need for exogenous growth factors (e.g., erythropoietin)

Note: Subjects who fulfill all the criteria for a CR (including bone marrow criteria) but who have a persistent anemia, thrombocytopenia, or neutropenia or a hypocellular bone marrow that is related to prior or ongoing drug toxicity (and not to CLL/SLL) will be considered as a CR with incomplete marrow recovery (CRi).

2.5.3 Partial Response

To satisfy criteria for a PR, all of the following conditions must be attained:

No evidence of new disease

Version 9, 18 Feb 2020

- A change in disease status meeting ≥ 2 of the following criteria, with 2 exceptions in which only 1 criterion is needed: (1) Only lymphadenopathy is present at baseline; or (2) only lymphadenopathy and lymphocytosis are present at baseline; in these 2 cases, only lymphadenopathy must improve to the extent specified below:
 - Decrease in peripheral blood ALC by \geq 50% from baseline
 - o A decrease by $\geq 50\%$ from the baseline in the SPD of the index nodal lesions
 - o In a subject with enlargement of the spleen at baseline, a splenomegaly response as defined in Section 2.4.2
 - In a subject with enlargement of the liver at baseline, a hepatomegaly response as defined in Section 2.4.2
 - \circ A decrease by ≥ 50% from baseline in the CLL/SLL marrow infiltrate or in B-lymphoid nodules
- No index, splenic, liver, or non-index disease with worsening that meets the criteria for definitive PD
- Peripheral blood meeting ≥ 1 of the following criteria:
 - ANC \geq 1.5 x 10⁹/L or \geq 50% increase over baseline without need for exogenous growth factors (e.g., G-CSF)
 - Platelet count $\ge 100 \times 10^9$ /L or $\ge 50\%$ increase over baseline without need for exogenous growth factors
 - Hemoglobin \geq 10 g/L (11.0 g/dL) or \geq 50% increase over baseline without red blood cell transfusions or need for exogenous growth factors (e.g., erythropoietin)

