- K Assessment of disease status will be conducted with standard clinical measurements: PE, CBCs, bone marrow aspirates/biopsies, and imaging as appropriate for indication. During treatment, scans will be repeated for tumor assessment within 7 days of Day 1, Cycles 3, 5, and 7 then every 3 months until PD or use of alternative antineoplastic therapy. For subjects still in response after 1 year, intervals for radiographic surveillance may be every 6 months. Subjects with CLL who achieve CR will require assessment of MRD by flow cytometry of bone marrow and peripheral blood.
- L Imaging at EOT is not required if PD has already been radiographically documented or last imaging was within 30 days of EOT visit.
- M Subjects with CLL/SLL must provide either a fresh blood sample containing circulating tumor cells or a bone marrow aspirate sample pretreatment. Tissue will be submitted for evaluation of the percentage of tumor cells and analysis of genetic alterations and/or gene expression that may predict anticancer activity and/or pharmacodynamic activity. In addition, for subjects with CLL/SLL, the sponsor may arrange for a portion of the sample to be evaluated at a sponsor-specified laboratory for known prognostic markers (e.g., quantitative immunoglobulins, FISH panel [chromosome 11q deletion, 13q deletion, 17p deletion and 12 trisomy], DNA mutational analysis for p53, IgHV [including IgHV3-21], and other genes of interest in CLL [e.g., Notch]; flow cytometry [for CD5, CD10, CD11c, CD19, CD20, CD23, CD38, CD45, kappa and lambda light chains and ZAP-70], and/or β2-microglobulin). The baseline bone marrow aspiration procedure (if required) should be performed after the study candidate has undergone the baseline radiology examination and is otherwise considered eligible for study participation. All subjects with CLL/SLL must have baseline imaging (with CT scans [preferred] or MRI scans).

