- N Blood sampling for determination of the plasma concentrations and activity of apilimed-LAM-002A and metabolites will be performed on C1D1 and C1D8 as follows: pre-dose, 30 minutes, 1, 2, 4, 6, 8 hours post-first dose of the day. Sampling on C1D15 will be pre-dose only. Additional PK samples will be collected, if possible, whenever a subject has a study treatment related SAE or QTc > 500 msec. Subjects are required to come to the study site in a fasting state prior to the collection of certain PK samples. For analyte determination, PK back up sample will be used from time points: Cycle 1 Day 1 and Cycle 1 Day 8 pre-dose.

Protocol: LAM-002A-NHL-CLN01

Version 9, 18 Feb 2020

- O Bone marrow aspirates/biopsies performed within 2 months prior to first dose may be used for clinical baseline assessments. For subjects with NHL, baseline bone marrow biopsies/aspirates may be omitted if not deemed essential for response assessment or patient management and there is another source of tumor tissue for pretreatment evaluation of gene expression and prognosis. For subjects with CLL/SLL, a baseline bone marrow aspirate is required unless the presence of sufficient circulating cells in the peripheral blood (e.g., absolute lymphocyte count [ALC] $\geq 10 \times 10^9$ /L) permits assessment of baseline parameters as described in Footnote m, above.
- P If necessary per applicable response criteria, a repeat bone marrow biopsy or aspirate will be required for subjects who have a CR by imaging and physical examination.

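### In the CLL/SLL partial-response rule the lymphocyte criterion has no baseline condition, and one marrow-positive subset has no scheduled valid second criterion

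*Combined protocol and SAP*

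**What the plan says.** The rule is in Appendix 2, CLL/SLL part, Section 2.5.3 (Partial Response). It lists five improvements: ALC, nodal SPD, spleen, liver and marrow. A subject must meet at least two "of the following criteria, with 2 exceptions in which only 1 criterion is needed". The exceptions are lymphadenopathy alone, or the case where "only lymphadenopathy and lymphocytosis are present at baseline; in these 2 cases, only lymphadenopathy must improve to the extent specified below".

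The organ criteria carry a baseline condition. For the spleen it reads "In a subject with enlargement of the spleen at baseline, a splenomegaly response as defined in Section 2.4.2", and the liver is worded the same way. The ALC criterion reads only "Decrease in peripheral blood ALC by \geq 50% from baseline". The marrow criterion is a fall of at least half "from baseline in the CLL/SLL marrow infiltrate or in B-lymphoid nodules".

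On marrow data, Section 8.7, Table 8, footnote p says that, if the response criteria make it necessary, "a repeat bone marrow biopsy or aspirate will be required for subjects who have a CR by imaging and physical examination". Footnote k, attached to the imaging row, is broader: "Assessment of disease status will be conducted with standard clinical measurements: PE, CBCs, bone marrow aspirates/biopsies, and imaging as appropriate for indication".

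The only version of Section 2.5.3 available is inserted text in the amendment history, ahead of the Amendment 4 entries. The current appendix is in a part of the document not supplied. No later change appears in the pages available, but some pages were removed.

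**The concern.** A PR criterion should register a change in disease. Four of the five do so by construction: spleen and liver by an explicit condition, nodes because index lesions must be abnormal at baseline (Section 2.4.1), and marrow because it refers to the CLL/SLL infiltrate. ALC is the exception. A count that starts and ends below the plan's own CR limit of 4 x 10^9/L (Section 2.5.2) shows no lymphocytosis at either time, yet its halving counts as much as a halving of tumor. Section 2.5.6 already accepts that ALC can move without the tumor, since isolated lymphocytosis is not progression.

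The marrow gap works in the other direction. Documented infiltration removes the one-criterion route on a literal reading, while the marrow criterion has no mandated on-study data short of apparent CR.

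PR feeds the response rate (Section 14.3.1) and decides who enters the analyses of time to response and duration of response (Section 14.3.2).

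**Working it through.** The plan states no sample size, power or error rate for CLL/SLL response, so there is no figure to reproduce. The check applies the rule of Section 2.5.3.

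**Inputs**
- Five criteria, the two-criteria requirement and the two exceptions: Section 2.5.3.
- ALC limit for CR, below 4 x 10^9/L: Section 2.5.2.
- Spleen enlarged if above 12 cm by imaging; spleen and liver re-measured at stipulated intervals: Section 2.4.2.
- WBC differential repeated on schedule; marrow per footnotes k and p: Section 8.7, Table 8.

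**Step 1. Two illustrative subjects with the same tumor course.** Assume no new disease, nothing meeting PD, and the blood-count condition of Section 2.5.3 met. Baseline: SPD 20 cm², spleen 15 cm (enlarged), ALC 2.0 x 10^9/L. The enlarged spleen means that two criteria are needed.
- Nodes: SPD falls to 9, (20 − 9)/20 = 55%. Met in both.
- Spleen: unchanged at 15 cm. Not met in either.
- Subject A: ALC falls to 0.9, (2.0 − 0.9)/2.0 = 55%. Met. Total 2, so PR.
- Subject B: ALC falls to 1.2, (2.0 − 1.2)/2.0 = 40%. Not met. Total 1, so SD.

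Only the movement of a normal lymphocyte count separates the labels.

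**Step 2. How widely this applies.** Take nodal disease as present, and let lymphocytosis, splenomegaly, hepatomegaly and marrow disease each be present or absent: 2^4 = 16 baseline states. The exceptions cover the 2 with no spleen, liver or marrow disease, so 16 − 2 = 14 need two criteria. ALC is normal in half of those, 7.

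In these 7 states PR rests on the ALC fall when exactly one other criterion is met. The number of other criteria available is 1 (nodes) plus the number of abnormal compartments among spleen, liver and marrow:

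| Abnormal among spleen, liver, marrow | States | Patterns per state | Patterns |
|---|---|---|---|
| 1 | 3 | 2 | 6 |
| 2 | 3 | 3 | 9 |
| 3 | 1 | 4 | 4 |
| Total | 7 | | 19 |

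Thus 19 response patterns change from PR to not PR once ALC is conditioned on baseline lymphocytosis. In 7 the other criterion is nodal. In 12 (4 each for spleen, liver and marrow) there is no nodal response. These are unweighted patterns, not patient frequencies.

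**Step 3. The marrow gap.** With marrow disease present there are 2^3 = 8 states. Seven also have lymphocytosis, splenomegaly or hepatomegaly, each re-measured on schedule. That leaves 8 − 7 = 1: nodes plus marrow disease, normal ALC, no organomegaly. There the only second criterion that reflects disease is marrow, and every on-study cell of the Table 8 marrow row carries footnote p.

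**Step 4. The two parts interact.** In that one state the existing text still allows PR through a fall in the normal ALC. Conditioning ALC alone would close that route and leave only an unscheduled marrow. If marrow infiltration alone no longer removes the nodal-only route, nodes plus marrow, with or without lymphocytosis, joins the exceptions, and 14 − 2 = 12 states still need two criteria.

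**The case against.** The best defence is that the list is introduced as a change in disease status and that the second exception speaks of lymphocytosis at baseline, so a sensible assessor would not credit a fall in a normal count. That supports calling the change a clarification. It does not override an explicit criterion with no condition, next to two that have one.

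Several stronger readings are tempting, and the documents do not support them.
- *An ALC fall by itself produces PR.* It does not. Outside the exceptions it is one of two required criteria; inside them only nodes count.
- *Marrow is never re-measured.* It is repeated at apparent CR, and footnote k allows it as appropriate. What holds is that no repeat is mandated short of apparent CR.
- *Low-count subjects are those with documented marrow disease.* A baseline aspirate is required unless circulating cells suffice (for example ALC of at least 10 x 10^9/L), but it serves gene-expression and prognostic sampling. Having one does not show infiltration. On a limit of 4, subjects between 4 and 10 have lymphocytosis, and an ALC fall is valid for them.
- *Subject B is a responder wrongly called SD.* Two compartments were abnormal and one improved; SD is what a two-criteria rule intends. The fault is in subject A's label.
- *Steroid-induced lymphopenia drives CLL/SLL response.* Dexamethasone is required on the intermittent schedule (Section 6.8.2.6.2), but nothing in the documents quantifies an effect on ALC. The point does not rest on it.

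The timing objection stands in part. The extension-stage text provides for database lock, and changing a response definition late in an open-label trial invites the charge of post hoc relabelling.

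**Conclusion.** The concern holds in limited form. The ALC criterion can give a wrong PR in any of the 7 normal-ALC states that need two criteria, always together with exactly one other criterion. Under-assignment through the marrow gap is confined to 1 of 8 marrow-positive states, and the loose ALC criterion partly offsets it.

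The reach is small. The expansion cohorts (Section 6.1.2, Table 2) are FL, MZL and DLBCL, and the sequential ORR boundaries concern FL, so only CLL/SLL subjects of the dose-escalation stage are affected. Their number n is not given. As an assumption, one reclassified subject moves a CLL/SLL response rate by 100/n points: 33 at n = 3, 17 at n = 6, 10 at n = 10, 7 at n = 15. A reader might apply the first two figures to the escalation cohorts of 3 to 6, but those are DLT cohorts open to several histologies, and no CLL/SLL response rate per cohort is defined.

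The conclusion assumes that the current appendix carries the inserted wording, that documented marrow disease takes a subject out of the exceptions, and that 4 x 10^9/L is a fair threshold for lymphocytosis. That value is borrowed from the CR criterion; the pages available define no other.

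**What to change.** After confirming the current wording, make two changes to Section 2.5.3 together:
1. Begin the ALC criterion with: *In a subject with lymphocytosis at baseline (ALC ≥ 4 x 10^9/L)*.
2. Add to the exceptions that baseline marrow infiltration alone does not remove the nodal-only route to PR. Apply this in the same way whether or not marrow was repeated, so that a missing marrow cannot produce a PR that an unimproved marrow would deny.

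The first should not be adopted without the second, for the reason in step 4.

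Re-derive PR from baseline ALC, baseline marrow and the nodal, spleen and liver measurements already collected. If the Stage 1/2 database is locked, leave the labels under the existing text in place and report the re-derivation beside them as a sensitivity analysis.

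The cost is two phrases and a re-derivation, with no new procedures. A few PR/SD labels may change, and because the trial is open-label any late relabelling must be disclosed with its date and reason.
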